August 16, 2022

Do Generic Volar Locking Plates Provide Similar Outcomes at a Reduced Cost?

Study Protocol and Statistical Analysis Plan

Study Narrative

1. Summary

Distal radius fractures are a common injury in the community. When treated with open reduction internal fixation (ORIF), the volar locking plate (VLP) is the most frequent implant used. Current literature has shown most orthopaedic surgeons are unfamiliar with construct costs. Many surgeons use implants the hospital provides and have no preference for one implant company's plate over another. Previous studies have demonstrated increased implant costs do not increase patient reported outcomes (PROs) in other injury patterns. Generic implants can potentially reduce total procedural costs and not negatively impact patient outcomes. With an increasing emphasis being placed on providing high-value care to patients, and rising healthcare costs, there is a need to pursue more economical means of treating distal radius fractures. Additionally, with the increasing volume of distal radius fractures with a growing elderly population, it is important to consider adoption of an already partially implemented process. Some surgeons today in our health system use the generic VLP, with little apparent differences in reoperation rates and complications. Validation of its safety and efficacy on a larger scale could support its adoption as a universal stand of practice, thus reducing cost to the patient and hospital.

2. Study aims:

- a. Primary:
 - i. To determine if there is any difference in 90-day reoperation rate between patients treated with a generic or conventional volar locking plate.
 - ii. To determine if there is any difference in 90-day readmission rate between patients treated with a generic or conventional volar locking plate.
 - iii. To determine if there is any difference in 90-day mortality rate between patients treated with a generic or conventional volar locking plate.

- b. Secondary:
 - i. To determine if generic implants have a lower cost than conventional implants.
 - ii. To determine any differences in estimated blood loss by implant type (generic vs. conventional).
 - iii. To determine tourniquet time by implant type (generic vs. conventional).

3. Background, Rationale, Significance

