 - ii. All other standards of care remain equal between the groups.
- d. *Outcomes/endpoint and other variable definitions, and instruments used*
 - i. 90-day reoperation
 - ii. 90-day readmission
 - iii. 90-day mortality
 - iv. Implant cost
 - v. Estimated blood loss
 - vi. Tourniquet Time
- e. *Statistical analysis plan*
 - i. T-Tests and Chi-square of Demographic Data
 - ii. Chi-square of primary outcomes
 - 1. 90-day reoperation rate
 - 2. 90-day readmission rate
 - 3. 90-day mortality rate
 - iii. T-Test of Secondary Outcome Measures between subject groups
 - 1. Implant cost
 - 2. Tourniquet time
 - 3. Estimated blood loss
 - iv. Power analysis or statement of precision
An a priori power analysis was conducted to estimate the minimum sample size needed to adequately detect a difference in reoperation rates with a large effect size (Cohen's $d=0.8$). At a Type I error rate of 0.05, a power of 80%, and a 1:1

group allocation, the estimated sample size was 36 patients (18 generic VLPs vs. 18 conventional VLPs).

v. Strengths

1. Blinding of patients
2. Use of FDA approved devices
3. Randomizing of patients
4. Adequate qualified staff members to conduct the study
5. Surgeons will be adequately trained and reminded on the protocol and their specific research related duties.
6. High-volume surgeons who regularly treat distal radius fractures
7. Conservative effect size estimates

vi. Limitations

1. Surgeons are not blinded
2. Only early follow-up (90 days)
3. No patient reported outcomes included

5. Setting/Environment/Organizational feasibility

- a. This study will be conducted at Healthpartners within Minneapolis metropolitan area
- b. This HealthPartners setting has an appropriate patient population to carry out the proposed study.
- c. The orthopedic department leadership has been engaged in development and approval of this study

6. Risks and Benefits

- a. Potential risks
 - i. No different than associated risks of undergoing a standard DRF ORIF.
- b. Benefit to society
 - i. Being able to validate the use of cheaper implants to save cost for patients and healthcare systems.

7. Data Confidentiality and Privacy

- a. In order to secure patient confidentiality and data security, all data will be de-identified. All patients will be assigned a research identification number (not their MRN) that cannot be associated with their name, birthdate, or other identifying information.

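### Eighteen patients per group give about 65% two-sided power at d = 0.8, not the stated 80%, and d does not define a difference in reoperation rates

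*Combined protocol and SAP*

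**What the plan says.** The plan is a single combined document. Its only sample size justification is Section 4.e.iv, which sets out to "adequately detect a difference in reoperation rates with a large effect size", given there as Cohen's d = 0.8. The remaining inputs are "At a Type I error rate of 0.05, a power of 80%, and a 1:1" group allocation, and the result is that "the estimated sample size was 36 patients (18 generic VLPs vs. 18 conventional VLPs".

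Three other places bear on this:

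- Section 2.a.i words the first primary aim without direction: "To determine if there is any difference in 90-day reoperation rate between patients treated with a generic or conventional volar locking plate".
- Section 4.e.ii names the test: "Chi-square of primary outcomes", with 90-day reoperation first in the list. The t-tests in Section 4.e are for demographics, implant cost, tourniquet time and blood loss.
- Section 4.e.v lists "Conservative effect size estimates" among the strengths. The limitations in 4.e.vi do not mention power.

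The document gives no sidedness, no expected reoperation rate in either group, no conversion from d to a difference in proportions, and no allowance for dropout.

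**The concern.** There are two separate faults. First, d = 0.8 with 5% error and 80% power is a standard textbook case, and its answer is well above 18 per group. Second, d is a difference in means divided by a standard deviation. Without a base rate it does not say what difference in reoperation rates the trial is meant to detect, and the planned test is not a test of means.

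The stakes are high here because the plan hypothesises no difference in clinical outcomes (Section 3) and hopes to support wide adoption of the generic plate (Section 1). A non-significant chi-square is therefore the hoped-for result. A reader told that the trial had 80% power on conservative assumptions would take that result as evidence of similar safety, when at 36 patients the test would usually miss even a tripled reoperation rate. Assuming a large effect makes the required sample small, which is the opposite of conservative.

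**Working it through.** **Inputs from Section 4.e.iv:** d = 0.8, α = 0.05, power 0.80, 1:1 allocation, stated n = 18 per group. Sidedness is not stated. The aim in Section 2.a.i is non-directional, so two-sided is the natural reading; one-sided is shown as well.

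**1. Attempt to reproduce 18 per group, taking d literally.**

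Normal approximation: n per group = 2(z_α + z_β)² / d².

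- Two-sided: 2(1.960 + 0.842)² / 0.64 = 24.5, so 25.
- One-sided: 2(1.645 + 0.842)² / 0.64 = 19.3, so 20.

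The noncentral t calculation gives 25.52, so 26 (two-sided), and 20.03, so 21 (one-sided).

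**2. Power at 18 per group.** The noncentrality is d√(n/2) = 0.8 × √9 = 2.4.

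- Two-sided: Φ(2.4 − 1.96) = Φ(0.44) = 67.0%; noncentral t 64.5%.
- One-sided: Φ(2.4 − 1.645) = 77.5%; noncentral t 76.0%.

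For 80% two-sided power at 18 per group, d would have to be about 0.96.

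**3. Other readings of the effect size.**

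| Reading | Required for 80% | Power at 36 patients |
|---|---|---|
| Two-sided t, d = 0.8 | 52 total | 64.5% |
| One-sided t, d = 0.8 | 42 total | 76.0% |
| Cohen's h = 0.8 (normal approximation) | 50 total | 67.0% |
| Chi-square, w = 0.371 (d converted: 0.8/√(0.64 + 4)) | 57 total | 60.6% |
| Chi-square, w = 0.5 (the conventional large effect) | 32 total | 85% |
| Wilcoxon, two-sided | 54 total | – |

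None of these gives 36.

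**4. The scale actually analysed.** The document gives no reoperation rate, so the base rates below are assumptions. Power is by exact enumeration of two binomials with 18 per group at the two-sided 5% level.

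Generic rate at which power reaches 80%:

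| Assumed conventional rate | Uncorrected Pearson | Fisher exact |
|---|---|---|
| 1% | 31% | 37% |
| 2% | 34% | 40% |
| 5% | 42% | 47% |
| 10% | 51% | 56% |

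Power for particular differences from an assumed 5%:

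- h = 0.8 corresponds to 5% versus 34%: 64% Pearson, 50% Fisher.
- d = 0.8 converted to an odds ratio is exp(0.8π/√3) = 4.27, which is 5% versus 18%: 21% Pearson, 10% Fisher.
- 5% versus 15%: 13% Pearson, 5% Fisher.

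A direct illustration: suppose no patient in one group has a reoperation. With 3 of 18 in the other group, Pearson's statistic is 36 × 54² / (18 × 18 × 3 × 33) = 3.27, below 3.84. With 4 of 18 it is 36 × 72² / (18 × 18 × 4 × 32) = 4.50. So at least 4 of 18 (22%) would need reoperation, against none, before the test is significant.

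**The case against.** The best defence is that d = 0.8 is a slip for a large effect in general. On the chi-square scale the conventional large effect is w = 0.5, which needs only 32 patients and gives about 85% power at 36. That is true, but it is not the effect size printed and it does not produce 36. Nor does it make the target realistic. For equal groups w = (p₂ − p₁) / (2√(p̄(1 − p̄))), so with p₁ = 5% and p₂ = 49.6%, p̄ = 27.3% and w = 0.446 / (2 × 0.4455) = 0.50: about half of the generic group would need reoperation.

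A second defence is that sidedness is unstated and a one-sided test narrows the gap. It does, to 76.0% (77.5% by normal approximation), but this still falls short of 80%, needs 40 to 42 patients, and does not fit an aim of finding any difference.

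Third, 36 is described as a minimum, and Section 8 defines enrolment by calendar dates, so more patients might be enrolled. This stands: the power figures here apply at 36 patients and should be labelled so.

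Fourth, any restated figure depends on an assumed base rate and on the form of the test. At 5% versus 42%, power is 81% by uncorrected Pearson, 69% by Fisher and 66% with Yates' correction. This also stands and is reflected in the fix.

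**Conclusion.** The concern holds. With d taken as printed, 18 per group gives 64.5% power two-sided, against 80% claimed, and the sample that would deliver 80% is 52, not 36. The one-sided reading does not rescue the claim. This part needs no outside assumption beyond sidedness.

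The second part holds whatever the sidedness: d = 0.8 does not define a difference in a binary endpoint tested by chi-square. How weak the trial is on that scale depends on base rates that the document does not supply, but across assumed conventional rates of 1% to 10%, 36 patients give 80% Pearson power only against generic rates of about 31% to 51%. These figures treat patients as individually randomised. Sections 4.a and 4.c allocate whole calendar months, and no allowance is made for this or for dropout; neither would raise the power.

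Describing the effect size as conservative contradicts the plan's own description of it as large.

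**What to change.** 1. Replace the power statement in Section 4.e.iv with one on the proportion scale that names the test and labels its assumptions. For example:

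   > At 36 patients (18 per group), a two-sided 5% t-test has about 65% power for a standardised mean difference of 0.8; 80% power requires a difference of about 0.96. For 90-day reoperation, by uncorrected Pearson chi-square, 80% power is reached only for generic rates of about 34%, 42% and 51% against assumed conventional rates of 2%, 5% and 10%. Fisher's exact test requires about 40%, 47% and 56%. These figures ignore allocation by calendar month and loss to follow-up.

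2. Drop the 80% claim, or state the effect for which it holds.
3. Delete the effect-size item from the strengths in 4.e.v, and add to 4.e.vi that the trial has low power for plausible differences in reoperation, so a non-significant result does not show similar safety.
4. Make the same correction in the manuscript's sample size paragraph.

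The cost is wording only. No extra enrolment or change of analysis is needed, but the stated power becomes less favourable.

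### The effect size listed as conservative in Strengths is the one the power paragraph calls large, so the label overstates what a null result could show

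*Combined protocol and SAP*

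**What the plan says.** Section 4.e.iv (power analysis) sizes the trial to "adequately detect a difference in reoperation rates". It describes the target as a "difference in reoperation rates with a large effect size", with Cohen's d set at 0.8. With a 5% type I error rate, 80% power and equal allocation, it arrives at 36 patients, 18 per arm.

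Section 4.e.v, the next item, gives as its seventh strength "Conservative effect size estimates". No other effect size is stated anywhere in the document, so that entry can only refer to d = 0.8.

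Four other statements bear on how the label will be read:

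- The first primary aim is two-directional: "To determine if there is any difference in 90-day reoperation rate" (section 2.a).
- Section 3 hypothesises no difference in clinical outcomes.
- Section 4.e.ii tests the primary outcomes by chi-square. No equivalence or non-inferiority margin is given.
- Section 6.b gives validation of cheaper implants as the benefit to society.

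The Limitations (section 4.e.vi) cover unblinded surgeons, short follow-up and the absence of patient-reported outcomes. They do not mention sample size or detectable effect.

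**The concern.** In sample-size planning, an effect-size assumption is conservative when it is on the small side: the trial is then large enough even if the true difference is modest. Planning on a large effect does the reverse. The document applies both descriptions to the same number.

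In a superiority trial hoping for a positive result, this would be a small slip. Here a non-significant result is the hoped-for one, and no margin says how much excess reoperation would be tolerable. How much a null result means then depends on which differences the trial had a fair chance of detecting. Calling the planning effect conservative suggests that modest differences were provided for, and nothing in the Limitations corrects that.

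**Working it through.** **Inputs.** From section 4.e.iv: d = 0.8, alpha 0.05, power 80%, 1:1 allocation, 18 per arm. Sidedness is not stated; two-sided is used because the aim is any difference. The document gives no baseline reoperation rate, so 2%, 5% and 10% are assumptions for illustration. Month-by-month allocation is ignored throughout.

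**1. The plan's own figure.** The normal approximation gives n per arm = 2[(1.960 + 0.842)/0.8]² = 24.5, rounded up to 25, or 50 in total. The two-sided t-test gives 25.5, rounded up to 26, or 52 in total. One-sided versions give 40 and 42. None returns 36. That discrepancy is separate from the present point: with 52 patients the label would still be wrong.

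**2. What a more conservative choice would have required** (same formula, two-sided, 80% power):

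| Planned d | Total N, normal | Total N, t-test | Power at 18 per arm, t-test |
|---|---|---|---|
| 0.8 | 50 | 52 | 64.5% |
| 0.5 | 126 | 128 | 31% |
| 0.2 | 786 | 788 | 9% |

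Smaller effects mean larger trials, so 0.8 is the least demanding of the three.

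**3. Power at d = 0.8 with 18 per arm.** The standardised shift is 0.8 × √(18/2) = 2.4. The normal approximation gives Φ(2.4 − 1.96) = 67.0%; the t-test gives 64.5%. The effect detectable with 80% power is (1.960 + 0.842) × √(2/18) = 0.93 (normal) or 0.96 (t-test), larger than the planned 0.8.

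**4. What 0.8 could mean for a rate.** Cohen's d describes means, so it has to be translated for a binary outcome. Two readings:

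- Cohen's h = 0.8: p₂ = sin²(arcsin√p₁ + 0.4).
- Logit-scale d: odds ratio = exp(0.8π/√3) = 4.27.

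Power below is by exact enumeration of the uncorrected chi-square at 18 per arm.

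| Assumed p₁ | p₂, h = 0.8 | Power | p₂, odds ratio 4.27 | Power | Doubling: power |
|---|---|---|---|---|---|
| 2% | 27% | 61% | 8% | 4% | 0.4% |
| 5% | 34% | 64% | 18% | 21% | 4.3% |
| 10% | 44% | 65% | 32% | 37% | 12% |

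Section 4.e.ii does not say whether a continuity correction applies; one could only lower these figures.

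**5. Size of a doubling against the planned effect.** For 5% to 10%, h = 2arcsin√0.10 − 2arcsin√0.05 = 0.19, and 0.19/0.8 = 0.24, so under a quarter of the planned value. The odds ratio is (0.10/0.90)/(0.05/0.95) = 2.11, against 4.27. On either reading a doubling is well below the planned effect. At 80% power it would need 435 per arm.

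**6. What a clean null would leave open.** With 0/18 events in both arms, the 95% Newcombe interval for the difference has limits ± z²/(n + z²) = 3.84/21.84 = 0.176, or about −18 to +18 percentage points.

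**The case against.** The strongest reply is that this is one entry in a list of strengths. It changes no endpoint, test, estimate or patient, and the value 0.8 and the word large are printed just above it, so nothing is hidden. Non-significance would come from few patients and few events, not from an adjective. All of that stands, and it makes this a correction of wording, not of the analysis. It does not make the entry true.

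Several stronger readings are tempting but not supported:

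- **That 0.8 is the least conservative value possible.** It is so only among the conventional small, medium and large benchmarks (0.2, 0.5, 0.8). A higher value would be less conservative still.
- **That readers will be misled.** That is an inference. The design makes it plausible, but the document cannot show it.
- **That the trial was sized only for a very large harm.** The aim covers a difference in either direction. On the rate scale, the assumed effect runs from 6 points (2% to 8%) to 34 points (10% to 44%), depending on the reading and the assumed baseline.
- **That the plan itself expected a small effect and should have used one.** The Summary's remark, "with little apparent differences in reoperation rates and complications", is an informal observation about current use. A planning effect may be the smallest difference worth detecting, which need not be the one expected. The contradiction does not need this support.
- **That smaller differences cannot be detected at all.** Low power is the accurate description.
- **That power for a doubling is about 1%.** That is the Fisher exact figure for 5% against 10%, and Fisher is not the planned test.

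**Conclusion.** The point holds as a contradiction within section 4.e: the planning effect is called large in one item and conservative in the next, and only the first description fits. This rests on the text alone and needs no assumed rate.

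Its importance comes from the design. With a no-difference hypothesis, a chi-square without a margin and a validation aim, the label overstates what a null result can show. At an assumed 5% baseline, a doubling has about 4% power by uncorrected chi-square with 18 per arm; at 2% and 10% the figures are 0.4% and 12%. Even the stated d = 0.8 has about 64.5% power by a two-sided t-test, not 80%. The rate-scale figures depend on the assumed baselines, but power is low for a doubling at each of them.

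**What to change.** 1. Delete the seventh strength in section 4.e.v.
2. Add to section 4.e.vi: *The sample size was based on a large assumed effect and gives low power for smaller differences in reoperation, including a doubling; a non-significant result does not establish similarity.*
3. In section 4.e.iv, express the assumed effect as two reoperation rates, name the baseline and its source, and give the power that 18 per arm provides for that pair under the planned test. The wording should not imply 80% power at d = 0.8.

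The cost is a few lines of text and a less favourable description of the design. No extra patients, data or procedures are needed. If enrolment has closed, the same wording can go into the report.

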DRFs are a prime target for generic implant implementation, due to the relatively high incidence of DRFs (634,000 annually) (Mauk Orthop Clin North America 2018), and the substantial amount spent by Medicare each year on DRF management (\$385-\$535 million) (Ray JBMR 1997, Burge JBMR 2007). The purpose of this study was to assess for differences in implant cost, surgical characteristics, and 90-day clinical outcomes between patients treated with generic volar locking plates (VLPs) and conventional VLPs in the setting of a DRF. We hypothesized that there would be no difference in surgical characteristics (e.g., tourniquet times) or clinical outcomes (e.g., reoperation), however there would be reduced cost in the generic VLP group.

4. Approach

a. Study design

- i. This will be a prospective randomized controlled trial within Healthpartners in the greater Minneapolis area in Minnesota, to compare primary outcomes of subjects between generic and conventional volar locking plates in distal radius fracture patients. Group selection will be randomized month to month with generic plates being used one month and conventional plates the next.

i. Inclusion

1. >18 years old
2. Isolated DRF
3. Medical need for surgical fixation with a volar locking plate

ii. Exclusion

1. No VLP used
2. Additional fixation used
3. Injury was non-isolated (polytrauma)
4. < 18 years old
5. Open fracture

- b. Data collection process
 - i. Identify patients within HealthPartners who meet inclusion criteria who are determined to need distal radius ORIF
 - 1. Patients meeting inclusion criteria will be identified by the included surgeons on the study
 - ii. Consent
 - 1. Written informed consent for surgery will be obtained by the attending surgeon, however no additional consent will be needed as this is an FDA approved device
 - iii. Data sources needed for this study
 - 1. Chart Review for patient age, gender, height and weight
 - 2. Chart review for mortality, reoperation, readmission
 - 3. Chart review for implants, tourniquet time, estimated blood loss
 - 4. Implants will be cross referenced with institutional charge master database to obtain cost.
 - iv. Process steps for data acquisition
 - 1. Data to be obtained by chart review after completion of the study.
- c. Intervention, treatments
 - i. Patients will be randomized by month with patients during one month receiving generic implants and the following month they receive conventional implants.

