- b. Patient information will only be accessed via secure servers for TRIA and on encrypted password-protected computers. If it is necessary to transmit patient data, it will be transmitted in the de-identified format, using only patient research identification numbers.
- c. At the end of the study, the electronic files will be permanently deleted and patient identifiers will be removed.

8. Timeline

- a. August 2022: IRB submission
- b. September 2022: IRB approval
- c. October 2022: Protocol implementation
- d. April 2023: Patient enrollment closes
- e. May 2023: Data analysis
- f. July 2023: Manuscript preparation

- g. July 2023: Manuscript submission
- 9. Dissemination/Sharing Results/Integration and Impact
 - a. We do plan on publishing to peer reviewed orthopedic journals such as;
 - i. The Journal of Bone and Joint Surgery
 - ii. Clinical Orthopedics and Related Research
 - iii. Journal of Orthopedic Trauma
 - b. We plan to disseminate the information on a local and regional level by presenting at;
 - i. University of Minnesota Grand Round
 - ii. Minnesota Orthopedic Society poster presentation
 - iii. Mid-America Orthopedic Society poster presentation
 - c. Results will be shared with HealthPartners

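### The timeline puts the analysis in May 2023, before patients operated on in April can reach day 90 for any of the three primary outcomes

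*Combined protocol and SAP*

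**What the plan says.** Section 2.a sets three primary aims with the same window. The first reads "To determine if there is any difference in 90-day reoperation rate between patients treated with a generic or conventional volar locking plate"; the other two put the same question for readmission and mortality. Section 4.d lists the same three 90-day endpoints, and the limitations in section 4.e.vi describe follow-up as 90 days.

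Section 8 gives one month per milestone, without days:

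- "October 2022: Protocol implementation"
- "April 2023: Patient enrollment closes"
- "May 2023: Data analysis"
- "July 2023: Manuscript submission"

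No follow-up period is listed between the close of enrolment and the analysis.

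On data capture, section 4.b.iv says only "Data to be obtained by chart review after completion of the study". Study completion is not defined. The analysis in section 4.e.ii is "Chi-square of primary outcomes", with no rule for a patient who has been observed for less than 90 days. Allocation (section 4.a) is by calendar month, with "generic plates being used one month and conventional plates the next".

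**The concern.** A 90-day proportion needs every patient in the denominator to have been at risk, and observed, for 90 days or until the event. On the dates given, the latest patients would not have been. A chi-square test on crude counts has no means of censoring them, so their unobserved days would pass as event-free and the observed rates would be too low.

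Two features of this trial add to the problem. First, the authors expect no difference in clinical outcomes and want to support wider use of the generic plate; missed events lower the very rates on which that reassurance would rest. Second, plates alternate by month, so a shortfall confined to the last months falls on particular arms and need not be equal between them.

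**Working it through.** The plan states no figure for this point, so there is none to reproduce. The check is calendar arithmetic.

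**Inputs from the documents.** Outcome window 90 days (sections 2.a and 4.d); start October 2022, close April 2023, analysis May 2023 (section 8); monthly alternation (section 4.a); 18 patients per arm, 36 in total (section 4.e.iv, a minimum and not a stated total).

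**Assumptions.** Even accrual from 1 October 2022, surgery on the day of enrolment, strict alternation, last surgery on 31 March, 15 April or 30 April, and data cut on 1 May or 31 May. The documents give no event rate, so I use 2% to 10% per outcome, with events spread evenly over the 90 days.

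**Step 1: the gap.**
- Longest gap for an April surgery: 1 April to 31 May = 60 days. Shortest: 30 April to 1 May = 1 day. A last surgery on 31 March gives 61 days to 31 May.
- Day 90: 1 April + 90 = 30 June; 15 April + 90 = 14 July; 30 April + 90 = 29 July.
- Working backwards, complete outcomes need the last surgery by 31 January (1 May cut) or 2 March (31 May cut).

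**Step 2: patients short of 90 days, and person-time lost.** Share incomplete = surgery days less than 90 days before the cut / all surgery days. Unobserved person-time = 1 − mean(min(90, cut − surgery)) / 90.

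| Last surgery | Cut | Incomplete | Unobserved person-time | October-start arm vs other arm (person-time) |
|---|---|---|---|---|
| 31 March | 1 May | 59/182 = 32.4% | 10.8% | 5.0% vs 16.5% |
| 31 March | 31 May | 29/182 = 15.9% | 2.7% | 0% vs 5.3% |
| 15 April | 1 May | 74/197 = 37.6% | 15.7% | 14.9% vs 16.5% |
| 15 April | 31 May | 44/197 = 22.3% | 5.6% | 5.9% vs 5.3% |
| 30 April | 1 May | 89/212 = 42.0% | 21.0% | 24.5% vs 16.5% |
| 30 April | 31 May | 59/212 = 27.8% | 9.3% | 12.4% vs 5.3% |

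A later start raises the share: accrual from 31 October to 30 April with a 1 May cut gives 89/182 = 48.9%.

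**Step 3: missed events.** Missed = patients × event rate × unobserved fraction.
- Low: 36 × 0.02 × 0.027 = 0.02.
- High: 36 × 0.10 × 0.21 = 0.76.
- Total expected, for comparison: 36 × 0.02 = 0.72 to 36 × 0.10 = 3.6.
- One event in an arm of 18: 1/18 = 5.6 percentage points.

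**Step 4: difference between arms.** The largest modelled gap is 16.5% − 5.0% = 11.5% (last surgery 31 March, 1 May cut). At 18 per arm this is 18 × 0.02 × 0.115 = 0.04 to 18 × 0.10 × 0.115 = 0.21 events. With a last surgery on 15 April the gap is at most 1.6%, or 18 × 0.10 × 0.016 = 0.03 events, and its sign changes with the cut date.

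**Step 5: later cuts.** A 1 July cut leaves 0/182 incomplete (last surgery 31 March), 0/183 (1 April), 13/197 = 6.6% (15 April) or 28/212 = 13.2% (30 April). A 31 July cut leaves none for any April close.

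**The case against.** Four points can be made for the plan.

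1. *The timeline is indicative.* With nothing listed for June, the May entry could mark the start of an analysis phase running up to the July manuscript, and every window closes by 29 July. This makes the 60-day limit conditional on data being cut in May. It does not remove the conflict: an analysis begun in May still precedes day 90 for any April surgery, and submission in July may do so too.

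2. *The close of enrolment is not the last surgery.* If the last operation fell by 2 March, a 31 May analysis would be complete. The plan sets no such limit, and surgery some days after enrolment would shorten the gap further.

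3. *Data are collected only once the study is complete, and follow-up is described as 90 days.* The natural reading is that completion includes follow-up. If so, the May date cannot be met and is wrong; if completion means the end of enrolment, the outcomes are incomplete. The text does not say which.

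4. *The harm is inferred and small.* This stands. The SAP does not say that partly observed patients would be counted as event-free; that follows from a crude chi-square with no rule. Fewer than one missed event per outcome is expected, and the upper figure combines the latest close, the earliest cut and the highest assumed rate. The background section cites literature from 2023 and 2024, so the text was revised after the title date of August 2022 and the May date may simply be out of date. Nothing in the documents shows that the analysis was actually run early.

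**Conclusion.** The concern holds. As dated, the plan contradicts its own outcome definition: no April surgery can reach day 90 by any date in May, and no other section corrects the schedule. That conclusion needs only the calendar and is firm.

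The consequence is less certain and probably modest. The 16% to 42% incomplete rests on even accrual from 1 October. The 0.02 to 0.76 missed events also rests on the assumed 2% to 10% event rates and on 36 patients. The imbalance between arms can go either way or nearly vanish, depending on the closing day, the cut date and which plate came first. All three primary outcomes are affected, and with so few events expected in total, one missed event would visibly change an arm's rate. The point should be corrected, but it is not a serious threat to the comparison.

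**What to change.** - In section 4.b.iv, define study completion and the chart-extraction cut-off as the last enrolled patient's surgery plus 90 days. For a last surgery between 1 and 30 April 2023 this is 30 June to 29 July 2023.
- In section 8, add the follow-up period, move the analysis to after that cut-off, and keep the manuscript dates after the analysis.
- In section 4.e.ii, add one sentence: the primary chi-square tests are run only after every patient has passed day 90.
- In section 7.c, files are deleted and identifiers removed at an end of study that is also undefined. State that the link to the chart is kept until the day-90 extraction is done, and reconcile this with section 7.a, which describes the research number as not traceable to the patient.

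The cost is a delay in the analysis of about one month (31 May to 30 June) to three months (1 May to 29 July), with the manuscript following and identifiers held for the same time. No patients, visits or procedures are added.
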